4.3.5 Examination of Subgroups

No subgroup-specific analysis is planned.

4.3.6 Interim Analysis

No formal interim statistical analysis is planned for this study. The Safety Review Committee (SRC) will perform ongoing reviews of safety, tolerability, and available PD data, with the primary purpose of protecting the safety of subjects/patients participating in this clinical study.

5 STUDY ENDPOINTS

Primary Endpoint

• The primary endpoint is the incidence of adverse events (AEs). Safety will also be evaluated through vital signs, electrocardiograms (ECGs), clinical laboratory assessments, and physical examinations.

Secondary Endpoints

For Part A, the secondary endpoints are:

- PK parameters including, but not limited to, maximum plasma concentration [C_{max}], time to reach maximum plasma concentration [t_{max}], area under the plasma concentration versus time curve [AUC], apparent terminal elimination half-life [t_½], fraction eliminated in urine [fe/F], and renal clearance [CL_R]
- Plasma and urine glycolate concentration

For Part B, the secondary endpoints are:

- First dose and steady state PK parameters including, but not limited to, C_{max} , t_{max} , AUC, $t_{1/2}$, fe/F, and CL_R
- Urinary oxalate excretion (oxalate content in 24-hour urine collection)
- Urinary glycolate excretion (glycolate content in 24-hour urine collection)
- Plasma glycolate concentration
- Calculated creatinine clearance

Exploratory Endpoints

The exploratory endpoints are:

- Plasma oxalate concentration
- I lasma oxalate concentration

Additional exploratory endpoints for Part B only are:

6 STUDY ASSESSMENTS

For both Part A and Part B, the assessments described in this section will be collected at assessment times throughout the course of the study. The exact frequency and timing of collection may be found in the Schedule of Assessments in Protocol ALN-GO1-001 (Amendment 4; 27 June 2017) for Safety and PD variables: Table 1 for Part A; Tables 2 and 3 for Part B monthly dosing, and Table 4 for Part B quarterly dosing. A detailed schedule of time points for the collection of blood and urine samples for PK analysis is in Protocol ALN-GO1-001 (Amendment 4; 27 June 2017) Table 10 for Part A and in Tables 11 and 12 for Part B. Detailed assessments will not be repeated in this document and it will be referred to herein as the Schedule of Assessments.

6.1 Safety Assessments

6.1.1 Adverse Events

An Adverse Event (AE) is any untoward medical occurrence in a patient or clinical investigational subject administered a medicinal product and which does not necessarily have a causal relationship with this treatment. AEs will be graded according to the CTCAE criteria (Version 4.0 or higher). Refer to CTCAE for unique clinical descriptions and additional information regarding grading of severity for specific AEs.

The Investigator is responsible for recording non-serious AEs that are observed or reported by the patient after administration of the first dose of study drug regardless of their relationship to study drug through the end of study. Non-serious AEs will be followed until the end of study.

The Investigator is responsible for recording SAEs that are observed or reported by the patient after the time when the informed consent is signed regardless of their relationship to study drug through the end of study. SAEs will be followed until satisfactory resolution, until baseline level is reached, or until the SAE is considered by the Investigator to be chronic or the AE is stable, as appropriate.

6.1.2 Vital Signs

Vital sign measurements include:

- Systolic and diastolic blood pressure (mmHg)
- Heart rate/Pulse rate (beats/min)

- Body temperature (°C)
- Respiratory rate (breaths/min)

6.1.3 Weight and Height

For all participants, height will be measured in centimeters. For Part B patients who are <18 years, height will be measured in triplicate and the mean value will be used to calculate the estimated glomerular filtration rate (eGFR) using the Schwartz Bedside Formula.

The variables recorded will include:

- Height (centimeters)
- Weight (kilograms)
- Body Mass Index (BMI) (kg/m²) which will be calculated from the height and weight measurement.

The baseline value for height for subjects in Part A and patients in Part B who are 18 years and older is defined as the last non-missing value before first dose of study drug; and for patients in Part B who are younger than 18 years old is defined as the mean of the last triplicate before first dose of study drug.

6.1.4 Physical Examinations

A full physical examination or a symptom-directed physical examination will be performed at selected time points, as described in the Schedule of Assessments.

A symptom-directed physical examination will include the evaluation of changes in symptoms or onset of new symptoms since the last visit.

6.1.5 Electrocardiograms (ECGs)

For both parts A and B, triplicate 12-lead ECGs will be measured 5 minutes apart at times indicated in the Schedule of Assessments. Recording will be obtained after the subject has rested comfortably in the supine position for approximately 10 minutes. ECGs should be performed at approximately the same time of day throughout the study. The Investigator (or designee) is responsible for reviewing ECGs and to determine the clinical significance of the results. The overall interpretation of the ECG will be recorded and any abnormality specified. The Investigator will provide a determination regarding the change from baseline ECG and specification of the change. The electrophysiological parameters assessed will include

- Rhythm
- Ventricular rate
- PR interval

- QRS duration
- QT interval
- ST and T waves
- Bazett-corrected QT interval (QTcB)
- Fridericia-corrected QT interval (QTcF)

All triplicate ECG measurements at a particular time point will be averaged prior to analysis and summarization.

6.1.6 Echocardiograms (Part B Only)

ECHO assessments will be performed according to instructions provided in a study manual at select time points outlined in the Schedule of Assessments. The Investigator or designee is responsible for reviewing the ECHOs to assess whether the results have changed since the Screening/Baseline visit and to determine the clinical significance of the results.

6.1.7 Clinical Laboratory Assessments

For both Part A and Part B, clinical laboratory tests will be evaluated at the times indicated in the Schedule of Assessments. Laboratory tests to be collected include:

- Hematology: Complete blood count with differential
- Serum Chemistry: Sodium, blood urea nitrogen (BUN), Creatinine and estimated glomerular filtration rate (eGFR) calculation (using the modification of diet in renal disease or Schwartz formula depending on age), uric acid, total protein, glucose, potassium, phosphate, albumin, calcium, carbon dioxide/bicarbonate, chloride
- Cardiac Enzyme: Troponin I
- Liver Function Tests: aspartate transaminase (AST), alkaline phosphatase (ALT), alkaline phosphatase (ALP), total and direct bilirubin
- Coagulation Panel: Prothrombin Time, Activated partial thromboplastin time, International Normalized Ratio
- Urinalysis: Visual inspection of appearance and color, pH (dipstick), specific gravity, Ketones, Albumin (optional), Glucose, Protein, Bilirubin, Nitrite, RBCs, Urobilinogen, Leukocytes, Microscopy (if clinically indicated)
- Immunogenicity: Anti-drug antibodies
- Pregnancy Testing: β-human chorionic gonadotropin (women of child bearing potential only). Serum testing will be performed at screening or menarche, and urinary screening thereafter.

The eGFR (in mL/min/1.73m²) will be calculated from serum creatinine (SCr) based on the Modification of Diet in Renal Disease (MDRD) formula for patients \geq 18 years of age and the Schwartz Bedside Formula for subjects \leq 18 years of age at enrollment.

MDRD Formula

Conventional units:

```
eGFR (mL/min/1.73m^2) = 175 \times (S_{Cr}[mg/dL])^{-1.154} \times (age)^{-0.203} \times (0.742, if female), or \times (1.212, if African American)
```

SI units

```
eGFR (mL/min/1.73m^2) = 175 \times (S_{Cr} [\mu mol/dL]/88.4)^{-1.154} \times (age)^{-0.203} \times (0.742, if female), or \times (1.212, if African American)
```

Schwartz Bedside Formula

Conventional units:

```
eGFR (mL/min/1.73m^2) = (.413 \times height [cm]) / Scr (mg/dL)
```

• SI units:

```
eGFR (mL/min/1.73m^2)= (36.2 \times \text{height [cm]})/ \text{Scr} (\mu \text{mol}/\text{dL})
```

All triplicate height measurements at a particular time point will be averaged and the mean will be used in the calculation of the eGFR.

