11.2. Formulae for Estimated Glomerular Filtration Rate Calculation

Estimated glomerular filtration rate (eGFR; in mL/min/1.73m²) will be calculated from serum creatinine (SCr) based on the Modification of Diet in Renal Disease formula for patients ≥18 years of age and the Schwartz Bedside Formula for patients <18 years of age.

Modification of Diet in Renal Disease Formula [10]

- Conventional units
 - $eGFR \text{ (mL/min/1.73m}^2\text{)} = 175 \times (\text{SCr [mg/dL]})^{-1.154} \times (\text{age})^{-0.203} \times (0.742, \text{ if female), or } \times (1.212, \text{ if African American})$
- SI units
 - $eGFR \text{ (mL/min/1.73m}^2\text{)} = 175 \times (\text{SCr } [\mu\text{mol/L}]/88.4)^{-1.154} \times (\text{age})^{-0.203} \times (0.742, \text{ if female), or } \times (1.212, \text{ if African American})$

Schwartz Bedside Formula [11]

- Conventional units
 - $eGFR \text{ (mL/min/1.73 m}^2\text{)} = (0.413 \times \text{height [cm]})/\text{Scr (mg/dL)}$
- SI units
 - $eGFR \text{ (mL/min/1.73 m}^2\text{)} = (36.2 \times \text{height [cm]})/\text{Scr } (\mu\text{mol/L)}$

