7.3.3 Demographic and Baseline Characteristics

In Part A and Part B, demographic and baseline characteristics will be summarized by regimen (as applicable in Part B) and ascending dose level groups, placebo, and in total for the Safety Analysis Sets. If the PK and PD Analysis Sets contain a different set of subjects/patients compared to those included in the Safety Analysis Set, then demographic information will be summarized separately for those analysis sets.

The following variables will be considered based on their collection at screening. Gender, race, and ethnicity will be summarized with contingency tables. Age at screening (years), height, weight, and body mass index (BMI) at baseline will be presented with appropriate summary statistics (n, mean, median, SD, minimum, maximum). See Section 6.1.3 for height and weight baseline definition. Patients <18 years of age at screening Part B will have the modified z-score calculated for their height, weight, and BMI according to the Centers for Disease Control growth chart [1] and will be presented with summary statistics.

For Part B patients, the 24-hour urinary oxalate excretion (mmol/24 hours/1.73m²) and eGFR at baseline will be summarized descriptively by dose level groups, placebo, and in total. Separate analyses will be provided for patients less than 18 years of age and patients 18 years or older at informed consent.

The number and percentage of subject who took vitamin B6 within 90 days of informed consent and/or during the study will be tabulated.

Summary tables will be presented by ascending ALN-GO1 dose level with subjects/patients receiving placebo pooled across enrollment cohort and in total.

By-subject data listings of demographic information will be presented for Part A and Part B.

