7.6 Pharmacodynamic and Exploratory Analyses

Pharmacodynamic parameters will be measured from blood and urine samples collected at times outlined in the Schedule of Assessments in both Part A and Part B. PD analyses will be based on the Pharmacodynamic Analysis Sets.

24-hour urine oxalate content corrected for BSA will be calculated as:

[24-hour urine oxalate in mmol/L]*[24-hour urine volume recorded in CRF in ml] /(1000 ml per L)*24hours/[actual collection time calculated from CRF in hours] *1.73/[patient BSA]

Where patient BSA will be calculated as:

Patient BSA = sqrt([mean height in cm] *[weight in kg]/3600).

24-hour urine creatinine clearance corrected for BSA will be calculated as:

[24-hour urine creatinine concentration in mg/dl]*[24-hour urine volume recorded in CRF in ml]

/[Plasma creatinine in mg/dl]/[actual collection time calculated from CRF in minutes] *1.73/[patient BSA]24-hour urine oxalate/creatinine ratio will be calculated as:

24-hour urine oxalate concentration (mg/L) /24-hour urine creatinine concentration (mg/dL)/10.

For Part A and Part B, the mean and standard error of actual values and changes from baseline in plasma and urine glycolate will be plotted over time by ALN-GO1 dose level and placebo. In

addition, plots will be provided for plasma and urine glycolate of individual subjects by dose level of ALN-GO1 and placebo.

For Part B, the mean and standard error of actual values and changes from baseline in urinary oxalate per 24-hour urine collection and urinary creatinine per 24-hour urine collection will be plotted over time. In addition, the plots will be presented separately by ADA status. Plasma glycolate concentration and oxalate/creatinine ratio will be plotted in the same manner. For patients randomized to placebo, figures will include PD measurements up to the first dose of open-label study drug.

For other PD variables in Part A and B, descriptive statistics will be provided for actual results, change from baseline, and percent change from baseline. For Part B, the PD summaries will be presented according to the data display specification in Section 7.2.3.For Part A and Part B, Cmax and AUCt of plasma glycolate will be presented with descriptive statistics and percent coefficient of variation [%CV]) by regimen and ascending dose level and placebo presented first.

In Part A and Part B, all PD data will be listed by regimen, dose, ADA status (Part B only) and subject/patient.

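### SAP 6.1.7 prints the wrong creatinine unit (µmol/dL) in both SI eGFR formulas and places 18-year-olds under both MDRD and Schwartz

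*SAP*

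**What the plan says.** SAP section 6.1.7 gives each eGFR equation in conventional and SI units. The conventional forms take creatinine in mg/dL. The SI form of MDRD is printed as "175 \times (S_{Cr} [\mu mol/dL]/88.4)^{-1.154" (followed by the age, sex and race terms), and the SI form of Schwartz as "36.2 \times \text{height [cm]})/ \text{Scr} (\mu \text{mol}/\text{dL". Protocol section 11.2 has the same constants with a different unit: "36.2 \times \text{height [cm]})/\text{Scr } (\mu\text{mol/L" for Schwartz, and likewise µmol/L for MDRD.

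On age, SAP 6.1.7 assigns MDRD to patients of 18 years and over, and the "Schwartz Bedside Formula for subjects \leq 18 years of age at enrollment". Protocol 11.2 has the "Schwartz Bedside Formula for patients <18 years of age", and protocol sections 5.1.3 and 7.1.1.2 use the same split.

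Elsewhere the SAP follows the protocol's cut. Section 6.1.3, which supplies the height for Schwartz, says "For Part B patients who are <18 years, height will be measured in triplicate". Section 7.3.3, for baseline urinary oxalate and eGFR, says "Separate analyses will be provided for patients less than 18 years of age and patients 18 years or older at informed consent". SAP section 9 declares no departures from the protocol's analysis.

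**The concern.** A stated analysis formula should give the right answer when followed literally, and an assignment rule should give each patient one formula. Here the SI formulas pair constants for µmol/L with a unit ten times larger, and the age rule gives an 18-year-old two formulas. Part B enrols ages 6 to 64, so an 18-year-old can enter.

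What is at stake is the descriptive eGFR output: the Part B baseline summary (SAP 7.3.3) and the on-study laboratory summaries (SAP 7.4.3). The SAP does not say whether the mg/dL or the SI form will be programmed for eGFR. With three patients on ALN-GO1 in each randomized Part B cohort, one patient's eGFR carries a third of the cohort mean.

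**Working it through.** **1. Which unit do the constants need?**

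Inputs: the SAP's own mg/dL constant for Schwartz (0.413), its SI constants (36.2 for Schwartz, 88.4 for MDRD), and protocol 11.2, which pairs 88.4 with µmol/L. So 1 mg/dL = 88.4 µmol/L = 8.84 µmol/dL.

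- Schwartz: 0.413 × 88.4 = 36.5, against 36.2 printed. The 0.8% gap is rounding, so the constant fits µmol/L. For µmol/dL it would have to be about 3.65.
- MDRD: dividing by 88.4 turns µmol/L into mg/dL. For µmol/dL the divisor would have to be 8.84.

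**2. Size of the error if creatinine is really converted to µmol/dL** (patient values are assumptions)

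| Assumed patient | mg/dL form | SI form, µmol/L | SI form, µmol/dL as printed |
|---|---|---|---|
| Child, 120 cm, 50 µmol/L (Schwartz) | 0.413 × 120 / (50/88.4) = 87.6 | 36.2 × 120 / 50 = 86.9 | 36.2 × 120 / 5 = 868.8 |
| Man, age 30, 100 µmol/L (MDRD) | 76.1 | 175 × (100/88.4)^-1.154 × 30^-0.203 = 76.1 | 175 × (10/88.4)^-1.154 × 30^-0.203 = 1084.9 |

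The inflation is exactly 10 for Schwartz and 10^1.154 = 14.26 for MDRD. If µmol/L values are entered and the printed label is ignored, the results are correct.

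**3. Age 18 under the two formulas** (sex, height and creatinine are assumptions)

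MDRD = 175 × SCr^-1.154 × 18^-0.203, times 0.742 for women. Schwartz = 0.413 × height / SCr. SCr is in mg/dL.

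| Assumed patient | SCr | MDRD | Schwartz | Difference |
|---|---|---|---|---|
| Man, 170 cm | 0.7 | 146.9 | 100.3 | 46.6 |
| Man, 170 cm | 1.0 | 97.3 | 70.2 | 27.1 |
| Man, 180 cm | 1.4 | 66.0 | 53.1 | 12.9 |
| Woman, 160 cm | 0.7 | 109.0 | 94.4 | 14.6 |
| Woman, 165 cm | 1.0 | 72.2 | 68.1 | 4.1 |
| Woman, 165 cm | 1.4 | 49.0 | 48.7 | 0.3 |

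For creatinine of 0.7 to 1.4 mg/dL, MDRD is therefore higher by about 13 to 47 mL/min/1.73m² in men of 170 to 180 cm, and by about 0 to 15 in women of 160 to 165 cm. One such man with creatinine 1.0 mg/dL in a group of three would move the group mean by 27.1 / 3 = 9.0.

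**The case against.** The strongest reply is that these are transcription slips with little route to a wrong result. Nothing else in either document uses µmol/dL. The mg/dL forms sit beside the SI forms, and the creatinine clearance formula in SAP 7.6 takes "Plasma creatinine in mg/dl". A programmer would most likely use mg/dL or enter µmol/L directly, and an eGFR of 869 or 1085 would be caught at once. This stands, and it is why the unit error ranks low.

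On age, the protocol states the cut clearly in three places, SAP 6.1.3 and 7.3.3 agree with it, and SAP section 9 implies that the protocol's rule was meant. The Part B schedules also stop measuring height after the end-of-treatment visit in patients of 18 and over, so Schwartz would lack a current height for them at later visits. All of this shows which rule was intended. It does not remove the contrary rule from the section a programmer would follow, and both values for an 18-year-old look plausible.

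Two smaller points. If the enrollment qualifier in SAP 6.1.7 covered only the Schwartz clause, a patient who turned 18 on study could also meet both rules; the more natural reading is that it covers both clauses. The less-than-or-equal sign could also be a fault in text extraction. However, strict under-18 wording is intact in SAP 6.1.3, and the wrong unit appears in two separate formulas.

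**Conclusion.** Both errors are present as written. The SI constants require µmol/L, by the SAP's own mg/dL formulas and by protocol 11.2. The age rule overlaps at 18, against the protocol and SAP 6.1.3, and neither difference is a declared change.

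The consequence is minor. The 10-fold and 14.3-fold inflation arises only if creatinine is converted to the printed unit. The age overlap matters only if a patient aged 18 at enrollment enters Part B, which the documents allow but do not show. Eligibility follows the protocol's formulas, and the adverse-event endpoint and creatinine clearance do not use the SAP's eGFR equations. The check establishes agreement within and between the two documents; it does not validate the equations against their sources.

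**What to change.** In SAP 6.1.7, replace µmol/dL with µmol/L in both SI formulas, and change the Schwartz age rule from 18 or under to under 18. This restores agreement with protocol sections 5.1.3, 7.1.1.2 and 11.2 and with SAP 6.1.3. Then confirm the creatinine input unit and the age cut in the eGFR program.

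The cost is three character-level edits and one program check. No new data are needed and there is no downside.

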6.1.8 Other Safety Variables

In Part A and Part B, testing for drugs of abuse will be conducted and judged at screening for participants \geq 18 years of age.

6.2 Pharmacokinetics Assessments

6.2.1 Sample Collections for Pharmacokinetic Analysis

Blood and urine samples will be collected for PK analysis at scheduled time points listed in Protocol ALN-GO1-001 (Amendment 4; 27 June 2017) Table 10 for Part A and in Table 11 and Table 12 for Part B.

6.2.2 PK Parameters

In Part A, PK parameters following single dose of ALN-GO1 (Day 1) will be characterized. In Part B, PK parameters following single and multiple doses (Day 1 and Day 57 for monthly dosing cohorts; Day 1 and Day 85 for quarterly dose cohorts) of ALN-GO1 will be calculated.

The following PK parameters will be calculated from the individual plasma concentration profiles ALN-GO1 by standard non-compartmental methods:

Parameters	Units	Description
C_{max}	ng/mL	Maximum observed plasma concentration
t_{max}	h	The time to reach the maximum observed concentration
AUC ₀₋₂₄	ng·h/mL	The area under the plasma concentration versus time curve, from time 0 to the 24 hour concentration (C_{24h}), as calculated by the linear trapezoidal method
AUC _{0-last}	ng·h/mL	The area under the plasma concentration versus time curve, from time 0 to t _{last} (time of last quantifiable concentration) as calculated by the linear trapezoidal method.
AUC _{0-inf}	ng·h/mL	The area under the plasma concentration versus time curve, from time 0 extrapolated to infinity, calculated as: $AUC_{0-inf} = AUC_{0-last} + C_{last}/\lambda z$ (Reported for Part A only)
AUC _{tau,ss}	ng·h/mL	Steady state area under the plasma concentration versus time curve, over the dosing interval at steady state (Reported for Part B only)
Lambda z (λ_Z)	h ⁻¹	Apparent terminal elimination rate constant calculated by linear regression of the terminal linear portion of the log concentration versus time curve
t _{1/2}	h	Apparent terminal elimination half-life, calculated as: $ln(2)/\lambda_Z$
CL/F	L/h	Total apparent body clearance after extravascular administration, calculated as: Dose/AUC _{0-inf}
CL/Fss	L/h	Total apparent body clearance at steady-state after extravascular administration, calculated as: Dose/AUC _{0-tau} (Reported for Part A only)
V _Z /F	L	Apparent volume of distribution based on the terminal elimination phase, calculated as: Dose/(AUC _{0-inf} × λ_Z) (for Part A) or Dose/(AUC _{0-tau} × λ_Z) (for Part B)

The following urine PK parameters will also be calculated:

Parameters	Units	Description
A _{e(0-24)}	mg	Cumulative amount of drug excreted in urine after dosing, calculated as the sum of $(C_{ur} \times V_{ur})$, where C_{ur} is the concentration in urine and V_{ur} is the volume of urine collected.
fe/F	%	Fraction eliminated in the urine, calculated as $(A_{e(0\text{-}24)}/Dose) \times 100$
CL_R	L/h	Renal clearance, calculated as A _{e(0-24)} /AUC ₀₋₂₄

In addition, Part B samples may also be used to characterize the

6.2.3 Pharmacokinetic Parameter Calculation

Actual sampling times, rather than scheduled sampling times, will be used in all computations involving sampling times.

The PK parameters λ_z , $t_{1/2}$, AUC_{0-inf} , CL/F, and V_z/F will not be presented for those subjects who do not exhibit a terminal elimination phase in their concentration versus time profiles. In order to estimate the apparent first-order terminal elimination rate constant, λ_z , linear regression of concentration in logarithm scale vs. time will be performed using at least 3 data points. Uniform weighting will be selected to perform the regression analysis to estimate λ_z . The constant λ_z will not be assigned if:

- The terminal elimination rate constant indicates a positive slope ($\lambda_z < 0$)
- T_{max} is one of the last 3 data points
- The adjusted regression coefficient (R²) is less than 0.8
- $t_{1/2}$ is more than half the total sampling interval

In cases where the λ_z interval is not assigned, the values of the associated parameters (λ_z , $t_{1/2}$, AUC_{0-inf} , CL/F, V_z/F , and possibly AUC_{0-24h}) will not be reported.

The linear trapezoidal method will be used in the computation of all AUC values. AUC_{0-inf} will be calculated as $AUC_{0-last} + C_{last,observed}/\lambda_z$, where $C_{last,observed}$ is the last observed evaluable plasma concentration.

